4.4. HANDLING OF MISSING DATA

No plasma concentration estimates will be imputed for missing values. Missing values will be treated as if they were not scheduled for collection and only those

samples with reported concentration values will be included in the pharmacokinetic and statistical analysis.

Missing values for urine collections will not be imputed. Any subject with a missing value for any subinterval (e.g. 0-1 hour) involved in the 0-6, 0-8 or 0-12 results will be excluded from statistical analyses for the interval affected.

No imputation of missing data will be done for any other data. To handle missing or partial AE and concomitant medication dates, the following rules in 5.4.1 will be applied.

4.4.1. For Partial Start Dates:

1. If the year is unknown, then do not impute the date but assign a missing value.
2. If the month is unknown, then:
 - i. If the year matches the year of the first dose date, then impute the month of the dose date.
 - ii. Otherwise, assign "January."
3. If the day is unknown, then:
 - i. If the month and year match the month and year of the first dose date, then impute the day of the dose date.
 - ii. Otherwise, assign "01."

4.4.2. For Partial End Dates:

1. If the year is unknown, then do not impute the date but assign a missing value.
2. If the month is unknown, then assign "December."
3. If the day is unknown, then assign the last day of the month.

After implementing the rules above, to determine whether AEs (or medications) with missing start or stop dates are pre-treatment or on/after first or second treatment, the following strategy will be used:

1. If both start date and stop date are missing, then the most conservative approach is taken, and the AE (or medication) is classified as treatment emergent (or concomitant medication).
2. If the start date is missing but the stop date is not missing and is on or after the day of study dose administration for Period 1 or 2, then the most conservative approach is taken, and the AE (or medication) is treatment emergent (or concomitant medication).
3. If the start date is missing but the stop date is not missing and is before the day of study dose for Period 1 and after the date of signed informed consent, then the AE (or medication) is not a TEAE (or prior medication).

4. If the start date is not missing but the stop date is missing, then the most conservative approach is taken, and medication is concomitant while the AE is defined by start date.

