6.2. Pharmacodynamic Endpoints

Urine will be collected from spontaneous voids in 1-hour increments for the first 8 hours and in 2-hour increments up to 12 hours post-dose. Total urine output, urinary sodium, and potassium excretion for each collection interval ((0-1), (1-2), (2-3), (3-4), (4-5), (5-6), (6-7), (7-8), (8-10) and (10-12) hours after initiation of dosing) will be recorded.

The following PD parameters will be evaluated for IV furosemide and SC SCP-111 subcutaneous administration:

Urine Output:

- Measured at 0-6 hours, 0-8 hours, and 0-12 hours
- The sum of urine output for intervals 0-1, 1-2, 2-3, 3-4, 4-5 and 5-6 comprise 0–6-hour urine output.
- The sum of urine output for intervals 0-1, 1-2, 2-3, 3-4, 4-5, 5-6, 6-7 and 7-8 comprise 0–8-hour urine output.
- The sum of urine output for intervals 0-1, 1-2, 2-3, 3-4, 4-5, 5-6, 6-7, 7-8, 8-10 and 10-12 comprise 0–12-hour urine output.

Urinary Sodium Excretion:

- Measured at 0-6 hours, 0-8 hours, and 0-12 hours
- Calculated as: Urinary Sodium Excretion=Total Urine Output (L) × Sodium Concentration (mEq/L)

Urinary Potassium Excretion:

- Measured at 0-6 hours, 0-8 hours, and 0-12 hours
- Calculated as: Urinary Potassium Excretion=Total Urine Output (L) × Potassium Concentration (mEq/L)

Example Calculation:

- **Interval: 0-1 hour**

Total Urine Output=0.5 L

Sodium Concentration=100 mEq/L

Urinary Sodium Excretion=0.5 L×100 mEq/L=50 mEq

- **Interval: 1-2 hours**

Total Urine Output=0.4 L

Sodium Concentration=90 mEq/L

Urinary Sodium Excretion=0.4 L×90 mEq/L=36 mEq

Continue this calculation for each subsequent interval (e.g., 0-1, 1-2, 2-3, 3-4, 4-5, 5-6, 6-7, 7-8, 8-10, and 10-12 hours) to obtain the total urinary sodium excretion for each time period.

Same calculations are conducted to calculate urinary potassium excretion for each interval.

The sum of intervals 0-1, 1-2, 2-3, 3-4, 4-5 and 5-6 comprise 0-6 hour urinary sodium/potassium excretion.

The sum of intervals 0-1, 1-2, 2-3, 3-4, 4-5, 5-6, 6-7 and 7-8 comprise 0-8 hour urinary sodium/potassium excretion.

The sum of intervals 0-1, 1-2, 2-3, 3-4, 4-5, 5-6, 6-7, 7-8, 8-10 and 10-12 comprise 0-12 hour urinary sodium/potassium excretion.

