9.2. Pharmacodynamic Analyses

Total urine output, total urinary sodium excretion, and total urinary potassium excretion from times 0-6, 0-8 and 0-12 hours will be tabulated by summing the concentration*volume of each collection interval across the time span specified and summarized using descriptive statistics including N, mean, standard deviation (SD), coefficient of variation (CV%), median, minimum, maximum, geometric mean and geometric CV% analyzed by treatment in the BA population.

A repeated measures, mixed model analysis will be used to evaluate the mean difference between SC and IV across all time points. This analysis will account for within-subject correlations and between-subject variability. The model will include fixed effects for treatment (SC vs IV), time, and treatment-by-time interaction, and a random effect for subjects.

- 95% Confidence Intervals (CI) for the difference between SC and IV administration will be calculated for all measured parameters.
- P-values will be determined for the comparison of subcutaneous and intravenous administration methods, using the mixed model analysis.
- The means and 95% CIs of the parameters will be plotted at the specified time points: 0-6,0-8 and 0-12 hr.

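### Could a urine interval with no void be counted as missing, so that subjects drop out of the sodium and potassium totals?

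*SAP*

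**What the plan says.** SAP 4.4 sets two rules for urine. The first is "Missing values for urine collections will not be imputed". The second is an exclusion: "Any subject with a missing value for any subinterval (e.g. 0-1 hour) involved in the 0-6, 0-8 or 0-12 results will be excluded". It is limited to the window concerned, since such a subject "will be excluded from statistical analyses for the interval affected". The term missing is not defined for urine.

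SAP 6.2 describes the collection: "Urine will be collected from spontaneous voids in 1-hour increments for the first 8 hours", then two 2-hour intervals up to hour 12. It also says that "Total urine output, urinary sodium, and potassium excretion for each collection interval" will be recorded. Excretion is defined interval by interval as volume times concentration, and the 0-6, 0-8 and 0-12 hour results are sums over 6, 8 and 10 intervals. SAP 9.2 describes the same calculation as "summing the concentration*volume of each collection interval across the time span specified". It then plans a mixed model with p-values and 95% confidence intervals "for the difference between SC and IV administration will be calculated for all measured parameters".

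Protocol 6.2.2.5 requires the volume to be documented for each collection period and an aliquot from each period to be sent for sodium and potassium.

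**The concern.** Neither document requires a void in every interval, so an empty one is possible. Its volume can be entered as 0, but there is no sample to assay and the concentration field stays blank. Read mechanically, a blank concentration makes the product blank, the no-imputation rule stops anyone from filling it, and the exclusion rule removes the subject from every window containing that interval. The subject would then be dropped although no urine was lost.

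That would matter in three ways. Two programmers could report different N and different means from the same data. Empty intervals are plausibly more common when output is low, so the exclusions might not be random. And the trial plans for only 18 completers, so a few exclusions would be noticeable. SAP 4.4 also speaks of a subject, without saying whether one missing interval removes the window in the affected period only or in both periods.

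**Working it through.** **1. The SAP's own example, extended.** SAP 6.2 gives 0.5 L × 100 mEq/L = 50 mEq for hour 0-1 and 0.4 L × 90 mEq/L = 36 mEq for hour 1-2. Both products reproduce. Now assume no void in hour 2-3. The volume is 0 L, so for any concentration c the excretion is 0 × c = 0 mEq, and the running sum is 50 + 36 + 0 = 86 mEq. The unknown c has no influence, so entering zero is not an imputation: the amount excreted in that interval is known.

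**2. Is the window total still right?** Each window result is the sum of what was voided inside it. Urine held during an empty interval is measured at the next void. If that void falls within the same window, the total is complete. If it falls after the window ends, the amount moves to a later window. That happens with spontaneous voids whichever way the empty interval is coded.

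**3. Do the two SAP formulas disagree?** SAP 6.2 writes volume × concentration and SAP 9.2 writes concentration × volume. They are the same product, so neither supports a different treatment of a zero volume.

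**4. What does the exclusion rule cover?** SAP 4.4 refers to missing values for urine collections. With volume documented for each interval under Protocol 6.2.2.5, a recorded 0 mL is a value. Urine that was spilled, lost or left unassayed is what lacks one.

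**5. What the mechanical reading would cost.** There is no planned figure to reproduce, because the documents give no no-void rate. Assume a probability p per interval, equal and independent across intervals. The share of subject-periods without a window result is 1 − (1 − p)^k, with k = 6, 8 or 10. For a gap in either period, the exponent for 0-12 hours is 20.

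| Assumed p | 0-6 h, per period | 0-8 h, per period | 0-12 h, per period | 0-12 h, either period |
|---|---|---|---|---|
| 1% | 5.9% | 7.7% | 9.6% | 18.2% |
| 2% | 11.4% | 14.9% | 18.3% | 33.2% |
| 5% | 26.5% | 33.7% | 40.1% | 64.2% |

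If only the four intervals after hour 6 can be empty, the 0-12 hour per-period shares fall to 3.9%, 7.8% and 18.5%, and the 0-6 hour result loses nobody. If no-void intervals count as zero, every entry is 0%.

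The table shows sensitivity to an assumption and predicts nothing. The independence assumption also sits badly with the worry in question: if empty intervals cluster in low-output subjects, fewer subjects are affected at the same p than the formula gives. The effect in mEq on the SC-IV difference, and its direction, cannot be derived from the documents.

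**The case for a change.** The best case for a change is that the text is silent. The only set-to-zero rule, in SAP 4.2, covers sample concentrations reported below the assay limit in the pharmacokinetic section; it does not reach a urine sample that never existed. The worked example in SAP 6.2 shows only intervals with urine. A literal programmer could regard entering zero as the imputation that SAP 4.4 forbids. SAP 9.2 goes beyond description to p-values and confidence intervals, so N matters, and a clarifying sentence would be cheap.

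The silence is real, and so is the second gap, between exclusion per period and exclusion per subject. What does not stand is the claim that two equally reasonable readings compete. The missing reading needs a documented zero volume to be disregarded and a blank product to go unquestioned. The second gap is also limited: the mixed model in SAP 9.2 has a random subject effect and does not need complete pairs, so it can use a subject's unaffected period. Finally, how a no-void interval is captured may already be settled in the eCRF or in the mock tables and listings that SAP 4.1 mentions, which were not available for this review.

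Timed voids at hours 6, 8 and 12 would not help here. They address urine carried over a window's end, not empty intervals inside a window. They would also depart from the spontaneous-void design and need a protocol amendment.

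**Conclusion.** No change to the plan follows. Neither document states the handling of a no-void interval, but recorded volume and the excretion formula together give 0 mL and 0 mEq, and an analyst following the plan would keep the window. On that reading no subject or subject-period is lost for this reason. The conclusion rests on sites entering 0 mL, as Protocol 6.2.2.5 implies, and not leaving the volume blank.

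Any effect would be confined to secondary pharmacodynamic endpoints, mainly sodium and potassium excretion, whose stated objective is descriptive. Urine output need not be affected, since volume is recorded for each interval, and the primary AUC comparison does not use urine data. Whether exclusion is per period or per subject is likewise a detail for the programming specification, and it matters only for urine that was truly lost or unassayed.

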6.2. Study Phases and Procedures

The Time and Event Schedule outlining study phases and procedures is provided in [Appendix 1](#).

The Screening Phase will be conducted on an outpatient basis between 14 and 3 days prior to Baseline. Subjects will be instructed to maintain a < 2 gram sodium diet and abstain from caffeine-containing products within 2 days prior to Baseline. Baseline/CRU Admission will occur on Day 0. Study drug will be administered on

Day 0 and Day 3 (± 1 day) with a 3 ± 1 day outpatient fluid washout phase between doses. Subjects will be instructed to continue a < 2 -gram sodium diet and abstain from caffeine-containing products through Day 0, the washout phase and Day 3 study drug administration. Follow-up visit will occur 24-48 hours after discharge from the CRU for Crossover Period 2.

Collection of the PK samples should occur as close to the scheduled time point as possible. The actual times of PK sample collections will be recorded. Assessments that are to be performed at the same time as a PK sample is to be drawn may be performed just prior to the collection of PK sample.

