7.7.8. Adverse Events and Serious Adverse Events during the Washout and Follow-up Period

If AEs emerge during the washout or Follow-up period, the causal relationship will be assessed in relation to the study treatment administered in the time preceding the washout or Follow-up period.

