2. STUDY DESIGN

This is an open-label, single-center, single-dose, randomized, two-way (two-period) crossover study in healthy volunteers. Each Subject will complete Screening, Baseline, Treatment (two cross-over periods), and Follow-up Phases.

The Screening Phase will be conducted on an outpatient basis between 14 and 3 days prior to the Baseline visit. Subjects will be instructed to maintain a < 2-gram sodium diet and abstain from caffeine-containing products within 2 days prior to admission to the Clinical Research Unit (CRU). On arrival to the CRU (Day 0), baseline and final qualification assessments will be performed.

The Treatment Phase will be comprised of two crossover periods separated by a 3 ± 1 day washout period. During each CRU admission and through the washout period, Subjects will continue a < 2-gram sodium diet and abstain from caffeine-containing products. At baseline (Day 0), subjects will be randomly assigned in a 1:1 ratio to 1 of 2 treatment sequences to receive intravenous (IV) furosemide or subcutaneous (SC) SCP-111 in the abdomen in Crossover Periods (i.e., IV followed by SC or vice versa). Blood samples will be collected to measure furosemide plasma concentrations at pre-dose and for 12 hours post-dose. Prior to dosing in each Treatment Phase, subjects will void their bladder completely and urine will be collected starting after the injection through 12 hours post injection to determine total urine output and urinary sodium and potassium excretion. Assessment of injection site pain will be conducted for IV and SC administration using an 11-point pain scale. Photographs of the injection site will be performed prior to the IV and SC injection (baseline) and 4 hours post IV administration and 6 hours post SC administration. In addition, a photograph will be taken of the IV and SC injection site for any adverse event (AE) (i.e., erythema, edema, pruritus, bruising) that occurs at the site at the time of the event. Subjects will remain domiciled in the CRU for each Treatment Phase through 12 hours after administration of study drug. After final assessments are performed, subjects may be discharged from the CRU if safety parameters are acceptable to the Investigator.

The Follow-up Phase will occur 24-48 hours (Day 5 ± 1) after discharge from the CRU following Crossover Period 2, completing Subjects' study participation.

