9.3.1. Adverse Events

Adverse events will be mapped to the Medical Dictionary for Regulatory Activities (MedDRA™) dictionary.

AEs will be assigned to each treatment period as follows:

- **Treatment-emergent AEs in Period 1**
 - All AEs with start date/time on or after the start of dosing in Period 1 and before the start of the washout period (if not missing) having been absent in pre-treatment (or) worsen in severity relative to the pre-treatment state following administration of study drug in Period 1.
 - AEs that emerge during the washout period and/or are causally related to the study treatment administered in the time preceding the washout period.

- **Treatment-emergent AEs in Period 2**
 - All AEs with start date/time on or after the start of dosing in Period 2 having been absent in washout period (or) worsen in severity relative to the pre-treatment state following administration of study drug in Period 2.
 - AEs that emerge during the Follow-up Phase and/or are causally related to the study treatment administered in the time preceding the Follow-up Phase.

AE summaries will be displayed by treatment for:

- **Overall AE Summary**
 - A general summary that includes all TEAEs reported throughout the study, regardless of the treatment period.
- **Period-Specific AE Summaries**
 - Separate TEAE summaries for each treatment period (1 and 2).

The AEs that occur prior to treatment in Period 1 will be summarized in listings and not included in TEAE summary tables. This helps in understanding their impact without confounding the safety profile of the specific treatment periods. All other adverse events will be considered 'pre-treatment'.

In the case where it is not possible to define an AE as being treatment emergent or not, the AE will be classified as treatment emergent as the most conservative approach.

Analyses of AEs will be performed for those events that are considered treatment emergent. The AE tables will include the number and percentage of subjects with at least one AE, the number of AEs by MedDRA primary SOC (sorted in decreasing order of the total frequency) and MedDRA PT (sorted in descending order of the total frequency within each SOC) unless otherwise indicated. A subject with more than one occurrence of the same AE in a particular SOC/PT will be counted only once in the total of those experiencing AEs in that particular SOC /PT.

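### An adverse event that starts in Period 2 with an unknown start day is normally dated to the Period 1 dose and tabulated under the other treatment, and the SAP has no tie-break

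*SAP*

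**What the plan says.** SAP 4.4.1 has a single anchor for partial AE start dates, the first dose date. For an unknown day: "If the month and year match the month and year of the first dose date, then impute the day of the dose date". In any other month the day is set to the first. For an unknown month: "If the year matches the year of the first dose date, then impute the month of the dose date", after which the day rule applies and gives the same dose date. The Period 2 dose date, the visit at which the event was first recorded and the stop date play no part in placing the start.

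The dosing days are set in Protocol 6.2: "Day 0 and Day 3 (± 1 day) with a 3 ± 1 day outpatient fluid washout phase". SAP section 2 likewise describes "two crossover periods separated by a 3 ± 1 day washout period".

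SAP 9.3.1 assigns events to periods mainly by start. Period 1 takes "All AEs with start date/time on or after the start of dosing in Period 1 and before the start of the washout period", and also "AEs that emerge during the washout period and/or are causally related to the study treatment administered in the time preceding the washout period". Period 2 takes events starting on or after its own dose. A further Period 2 bullet covers events that appear in follow-up, or that are related to the treatment given before follow-up. AE summaries are displayed by treatment.

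**The concern.** A single first-dose anchor suits a parallel-group trial, where the only question is whether an event began before or after treatment started. In a crossover the start date also decides which treatment the event is counted under. Here the second dose follows so closely that month and year rarely separate the periods. A Period 2 event with an unknown day is therefore pulled back to Day 0 and leaves the treatment under which it occurred.

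The AE tables by treatment are at stake, and describing the safety and tolerability of SCP-111 is a secondary objective. In a subject randomised to IV first, an event after SCP-111 could be counted under IV furosemide, and the reverse in the other sequence.

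**Working it through.** The documents state no figure on this point to reproduce, so the check applies the date rules to the dosing calendar.

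**Inputs**
- Imputation rule: SAP 4.4.1.
- Gap between doses, g = 2, 3 or 4 days: Protocol 6.2.
- Period assignment: SAP 9.3.1.
- Assumptions: first-dose dates spread over four calendar years (1,461 days, 48 months); true onset k = 0, 1 or 2 days after the Period 2 dose; the first dose date means the Period 1 dose.

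**Examples**
- Doses on 10 and 13 June, AE after the second dose recorded as June, day unknown. Month and year match, so the start becomes 10 June. That is the Period 1 dose date, and the event is charged to the other treatment.
- Doses on 30 June and 3 July, AE after the second dose recorded as July, day unknown. The month does not match, so the start becomes 1 July. That is in washout, which SAP 9.3.1 also charges to Period 1.

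**Same-month branch, onset on the Period 2 dose day (k = 0).** The event falls in a later month than the first dose only when the first dose is in the last g days of a month. Share dated to Day 0 = 1 − 48g/1461:
- g = 2: 1 − 96/1461 = 93.4%
- g = 3: 1 − 144/1461 = 90.1%
- g = 4: 1 − 192/1461 = 86.9%

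**First-of-month branch, k = 0.** The imputed first of the month precedes the second dose unless that dose is itself on the first. Further share placed before the second dose = 48(g − 1)/1461:
- g = 2: 48/1461 = 3.3%
- g = 3: 96/1461 = 6.6%
- g = 4: 144/1461 = 9.9%

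**Both branches.** The share meeting the Period 1 rule = 1 − 48(k + 1)/1461, whatever the gap:
- k = 0: 96.7%
- k = 1: 93.4%
- k = 2: 90.1%

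A direct count over all 1,461 dates gives the same percentages. All are conditional on a Period 2 AE with an unknown start day. They say nothing about how often that happens.

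**Do the follow-on rules in SAP 4.4.2 repair this?** They are introduced as sorting events into pre-treatment or on/after the first or second treatment. Their outcomes settle only whether an event is treatment emergent. Where the stop date is missing, the event is classified by its start date, which may be the imputed one.

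**Size in the tables.** Planned enrolment is 21, with 18 to complete. One subject is 1/21 = 4.8 to 1/18 = 5.6 percentage points, or about 5 per treatment in one table row. This is a maximum. A subject counts once per System Organ Class or Preferred Term, so the change disappears on either side if the subject has another event in the same row under that treatment.

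**The case against.** The strongest objection is that SAP 9.3.1 is not purely date-driven. The second Period 2 bullet does not depend on the imputed date. It can place in Period 2 an event reported at follow-up, or one judged related to the treatment given before follow-up. It would be too strong to say that the rule always gives the wrong treatment; the first-of-month branch is also right on a few dates. What remains is that an event caught by this bullet also meets the Period 1 date rule, and the SAP does not say which prevails.

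The design also makes partial dates unlikely. Subjects stay in the unit for 12 hours after each dose with continuous AE assessment, and AEs are asked about in washout, before Period 2 dosing and at follow-up 24 to 48 hours after discharge. This stands. Events recalled from the outpatient days or reported after the study are the likelier sources.

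Two stronger readings are tempting but unsupported:
- A reader might infer a conflict with Protocol 7.7.8. That section says that "the causal relationship will be assessed in relation to the study treatment administered in the time preceding the washout or Follow-up period". It concerns the causality judgement, not date imputation or table assignment, and the washout and follow-up bullets in SAP 9.3.1 follow the same principle.
- A reader might infer a bias towards one product, because the error always runs towards the subject's Period 1 treatment. Sequence is randomised 1:1, so that treatment is IV for about half the subjects and SC for the rest. The error blurs the comparison and does not favour SCP-111.

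**Conclusion.** The point holds as a minor defect in a stated rule. For a Period 2 AE with an unknown start day, SAP 4.4.1 and the date rule in 9.3.1 point to the Period 1 treatment for roughly 90% to 97% of calendar dates, given onset within two days of the second dose. Where the follow-up or causality bullet also applies, the SAP gives two answers.

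The likely effect is small. Few events should be involved, though the documents give no rate. AE results are descriptive, individual listings allow any such event to be traced, and the primary AUC analysis is untouched.

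The conclusion rests on reading the first dose date as the Period 1 dose. The SAP does not define it per period. A per-period reading would need the period to be known already, which is what a missing day leaves open.

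**What to change.** Amend SAP 4.4.1 for an AE whose unknown start day is consistent with either period. Impute the dose date of the latest period begun before the AE was first recorded, unless a reported stop date, the known month or the source record shows an earlier onset. Use only a reported stop date, because 4.4.2 sets an unknown stop day to the end of the month. State that this period assignment governs 9.3.1. If the period still cannot be determined, count the event under both treatments and flag it in the listing.

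The information is already collected: AEs are checked at the Pre-Period 2 assessment and again before Period 2 dosing (Protocol 6.2.1.5 and 6.2.1.6.1). An event first recorded after those checks is presumptively a Period 2 event.

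The cost is a few SAP sentences and a minor programming change. The downside is that a Period 1 or washout event reported late may be placed in Period 2, and an unresolved event is counted twice. The same edit can correct the cross-reference in SAP 4.4, which points to 5.4.1 although the rules are in 4.4.1.
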